APPENDIX 11. COAGULATION INDICES

For each coagulation time point in [Table 1](#), citrated plasma samples will be frozen for potential analysis of coagulation indices at a later date; these analyses may include, but may not be limited to, the indices listed in the following table:

Test Name	
Antithrombin Activity (ATIII Activity)	Fibrinogen Antigen
Partial Thromboplastin Time Mixing Studies	High-Molecular Weight Kininogen
D-dimer, quantitative	Prekallikrein
Euglobulin Lysis Time	Plasminogen Activator Inhibitor-1 Antigen
Factor II Activity	Plasminogen Activator Inhibitor-1 Activity
Factor V Activity	Plasmin-antiplasmin Complex
Factor VII Activity	Plasminogen Activity
Factor VIII Activity	Protein C Activity
Factor VIII Antigen Quantitation	Protein S Antigen Free
Factor IX Activity	Thrombin Time
Factor X Activity	Tissue Plasminogen Activator Activity
Factor XI Activity	Tissue Plasminogen Activator Antigen
Factor XII Activity	von Willebrand Factor Activity (Ristocetin Cofactor)
Factor XIII Activity	von Willebrand Factor Antigen
Fibrin Monomer	von Willebrand Factor Multimers
Fibrinogen Activity	

APPENDIX 12. SCHEDULE OF EVENTS FOR SUBJECTS WHO DISCONTINUE STUDY DRUG EARLY BUT AGREE TO RETURN FOR ASSESSMENTS AFTER THE ETD VISIT

	Assessment or Procedure	Monthly Day 1 (±5 days) ¹	Every 3 Months after Last Visit
Clinical	Prior/Concomitant Medications/Therapy	X	
	Adverse Event Assessment	X	
	Physical Exam ²	X	
	Vital Signs ³	X	
	ECOG PS/NYHA Class ⁴	X	
	NIS-LL & VASPI ⁵	X	
	SF-36v2 ⁶	X	
	KCCQ ⁷	X	
	6MWT ^{8,9}	X (Months 3, 6, 9, 12)	
	Echocardiogram ¹⁰	X (Month 12)	
	ECG (12-lead triplicate) ¹¹	X (Months 3, 6, 9, 12)	
Laboratory¹⁶	Hematology & Chemistry (including amylase and creatine kinase) ¹²	X	
	Coagulation ¹³	X	
	Inflammatory Biomarkers ¹⁴	X (Month 3) ¹⁵	
	Troponin T	X	
	NT-proBNP ⁸	X	
	Pregnancy (WOCBP)	X ¹⁷	
	Serum Free Light Chain	X (Months 3, 6, 9, 12)	
	Serum IFE & PEP	X (Months 3, 6, 9, 12)	
	Urinalysis – Dipstick ¹⁸	X (Months 3, 6, 9, 12)	
	Urinalysis - Quantitative/Renal Biomarkers ¹⁹	X (Months 3, 6, 9, 12)	
	24-hour Urine Collection:		
Urine IFE & PEP	X (Months 3, 6, 9, 12)		
Urine Protein Excretion	X (Months 3, 6, 9, 12)		
Other	Anti-NEOD001 Serum Sample	X ²⁰	
	Vital Status Phone Call		X ²¹

BP = blood pressure; ECG = electrocardiogram; ECOG PS = Eastern Cooperative Oncology Group performance status; ETD = Early Treatment Discontinuation; HR = heart rate; IFE = immunofixation electrophoresis; KCCQ = Kansas City Cardiomyopathy Questionnaire; NIS-LL = neuropathy impairment score – lower limbs; NT-proBNP = N-terminal pro-brain natriuretic peptide; NYHA = New York Heart Association; PEP = protein electrophoresis; RR = respiratory rate; 6MWT = 6-minute walk test; SF-36v2® = Short Form-36v2® Health Survey; VASPI = visual analog scale – pain intensity; WOCBP = women of childbearing potential.

1. Study visits will occur every 28 days based on scheduling from Month 1-Day 1. A ± 5 -day window is allowed for visits starting after Month 1. If a subject discontinues study drug prior to the end of the study, but is willing to continue to participate in study visits, the subject should have an ETD Visit per [Table 1](#) and then have assessments performed monthly, through Month 12, if willing. The most important visit is the Month 12-Day 1 Visit, so if a subject is unwilling to continue monthly visits, every effort should be made for the subject to return and complete the Month 12-Day 1 Visit on schedule. All visits after the ETD Visit should occur on schedule, that is, at the time when the visit would have occurred had the subject remained on study drug. An EOS Visit will not be conducted.
2. Conduct a directed physical examination, including weight, and the components of the exam as clinically indicated. Assess macroglossia, submandibular nodes/fullness, adenopathy, ecchymoses, liver/spleen size (palpable +/-), ascites (+/-), and edema (which should be quantified on a scale of 0-4).
3. Vital signs include HR, RR, BP, and body temperature; assess any time during visit after subject has been at rest ≥ 5 minutes.
4. See [Appendix 5](#) (ECOG) and [Appendix 6](#) (NYHA).
5. See [Appendix 3](#) (NIS-LL; for all subjects with peripheral neuropathy at Screening) and [Appendix 4](#) (VASPI; for subjects with painful peripheral neuropathy at Screening).
6. See [Appendix 7](#); SF-36v2 should be administered before performing any other study assessments on the same calendar day it is administered.
7. See [Appendix 8](#); administer KCCQ after the SF-36v2, but before conducting any other assessments on the same calendar day it is administered.
8. NT-proBNP should be drawn before conducting 6MWT if being performed on the same calendar day.
9. Collect BP and HR pre- and post-6MWT administration.
10. Perform echocardiogram locally within 10 days before Day 1.
11. Perform ECGs centrally any time during visit.
12. Hematology and chemistry per [Appendix 10](#).
13. Collect PT/INR and PTT monthly. Collect citrated plasma samples as clinically indicated for freezing and for potential analysis of coagulation indices at a later date; these analyses may include, but may not be limited to, the indices listed in [Appendix 11](#).
14. Inflammatory biomarkers per [Appendix 10](#).
15. Collect additional samples as clinically indicated, such as when significant toxicity occurs per protocol Section 5.4.2.
16. All laboratory tests to be done centrally, unless otherwise noted. Please refer to Laboratory Manual for details.
17. Obtain local laboratory serum pregnancy test 90 (± 5) days after the last study drug administration.
18. Per [Appendix 10](#).
19. Per [Appendix 10](#). It is important that the sample be taken before exercising and at approximately the same time for each collection; therefore, the first morning void is recommended. Urine samples will be collected and frozen for potential analysis at a later date.
20. Anti-NEOD001 serum samples: Collect if an earlier sample established the presence of anti-NEOD001 antibodies or if a subject discontinued treatment due to a suspected immunologic reaction.
21. For randomized subjects who received at least 1 dose of study drug, conduct vital status telephone call approximately 3 months after last visit and approximately every 3 months thereafter or until subject enrolls in a separate open-label study, death, or for up to 5 years.

APPENDIX 13. ANAPHYLACTIC REACTION SMQ

An Adverse Event or group of Adverse Events starting on the same day should be flagged as Anaphylactic Reaction per SMQ if the AE(s) meets one or more of the following criteria:

- Any term from Group A
- Any two terms, with one from Group B and one from Group C
- Any two terms, with one from Group D and one from either Group B or Group C

Group A Terms	
Preferred Term	Preferred Term Code
Anaphylactic reaction	10002198
Anaphylactic shock	10002199
Anaphylactic transfusion reaction	10067113
Anaphylactoid reaction	10002216
Anaphylactoid shock	10063119
Circulatory collapse	10009192
Dialysis membrane reaction	10076665
Kounis syndrome	10069167
Shock	10040560
Shock symptom	10040581
Type I hypersensitivity	10045240

Group B Terms	
Preferred Term	Preferred Term Code
Acute respiratory failure	10001053
Asthma	10003553
Bronchial oedema	10056695
Bronchospasm	10006482
Cardio-respiratory distress	10049874
Chest discomfort	10008469
Choking	10008589
Choking sensation	10008590
Circumoral oedema	10052250

Group B Terms	
Cough	10011224
Cyanosis	10011703
Dyspnoea	10013968
Hyperventilation	10020910
Irregular breathing	10076213
Laryngeal dyspnoea	10052390
Laryngeal oedema	10023845
Laryngospasm	10023891
Laryngotracheal oedema	10023893
Mouth swelling	10075203
Nasal obstruction	10028748
Oedema mouth	10030110
Oropharyngeal oedema	10078783
Oropharyngeal spasm	10031111
Oropharyngeal swelling	10031118
Pharyngeal oedema	10034829
Respiratory arrest	10038669
Respiratory distress	10038687
Respiratory failure	10038695
Reversible airways obstruction	10062109
Sensation of foreign body	10061549
Sneezing	10041232
Stridor	10042241
Swollen tongue	10042727
Tachypnoea	10043089
Throat tightness	10043528
Tongue oedema	10043967
Tracheal obstruction	10044291
Tracheal oedema	10044296
Upper airway obstruction	10067775
Wheezing	10047924

Group C Terms	
Preferred Term	Preferred Term Code
Allergic oedema	10060934
Angioedema	10002424
Erythema	10015150
Eye oedema	10052139
Eye pruritus	10052140
Eye swelling	10015967
Eyelid oedema	10015993
Face oedema	10016029
Flushing	10016825
Generalised erythema	10051576
Injection site urticaria	10022107
Lip oedema	10024558
Lip swelling	10024570
Nodular rash	10075807
Ocular hyperaemia	10030041
Oedema	10030095
Periorbital oedema	10034545
Pruritus	10037087
Pruritus allergic	10063438
Pruritus generalised	10052576
Rash	10037844
Rash erythematous	10037855
Rash generalised	10037858
Rash pruritic	10037884
Skin swelling	10053262
Swelling	10042674
Swelling face	10042682
Urticaria	10046735
Urticaria papular	10046750

Group D Terms	
Preferred Term	Preferred Term Code
Blood pressure decreased	10005734
Blood pressure diastolic decreased	10005737
Blood pressure systolic decreased	10005758
Cardiac arrest	10007515
Cardio-respiratory arrest	10007617
Cardiovascular insufficiency	10065929
Diastolic hypotension	10066077
Hypotension	10021097

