9.2. Adverse Events

Verbatim terms on eCRFs will be mapped to PTs and SOCs using MedDRA version 19.0. AEs will be reported and severity will be categorized using the Common Terminology Criteria for Adverse Events (CTCAE, Version 4.03).

Pretreatment AEs are those AEs with a start date prior to the first infusion of study drug. All AE summaries will be restricted to TEAEs, which are defined as any AE that newly appears, increases in frequency, or worsens in severity following initiation of study drug and through the last study visit or up to 30 days after date of last dose, whichever is later. If it cannot be determined whether the AE is treatment emergent due to a partial onset date, then it will be counted as such.

Each AE summary will be displayed by treatment group. Summaries that are displayed by SOC and PT will be ordered by descending order of NEOD001 incidence of SOC and PT within each SOC. Summaries of the following types will be presented:

- Overall summary of AEs including the number and percent of subjects with at least one of the following:
 - Any TEAE

- TEAE by maximum CTCAE Grade
- CTCAE Grade ≥ 3 TEAE
- Serious TEAE
- TEAE leading to death (outcome="Fatal" or severity=CTCAE grade 5)
- Treatment-related TEAE
- Treatment-related serious TEAE
- Treatment-related TEAE of CTCAE \geq Grade 3
- Treatment-related TEAE leading to death
- TEAE leading to infusion interruption
- TEAE leading to dose reduction of study treatment
- TEAE leading to dose being held
- TEAE leading to prolongation of infusion time (>2.5 hours)
- Infusion associated TEAE overall
 - Infusion associated TEAE with premedication concomitant medication for infusion related reaction
 - Infusion associated TEAE without premedication concomitant medication for infusion related reaction
- TEAE leading to study drug withdrawal
- Subject incidence of TEAEs by MedDRA SOC and PT. This summary will be repeated for all general and special baseline population subgroups defined in Section 6.
- Subject incidence of TEAEs by MedDRA SOC and PT occurring in $\geq 5\%$ of NEOD001 subjects with greater frequency than placebo.
- Subject incidence of TEAEs by MedDRA SOC and PT occurring in $\geq 10\%$ of NEOD001 subjects with greater frequency than placebo.
- Subject incidence of TEAEs by MedDRA SOC and PT occurring with greater frequency than placebo.

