9.2.1. Other Adverse Events: Infusion Reactions

The incidence of infusion associated TEAEs by MedDRA SOC and PT will be summarized by treatment group and presented in a listing. This is a subset of the AEs where the question “Was the event an infusion-associated adverse event?” is checked “Yes”. Summaries will be repeated for all general baseline subgroups indicated in Section 6.

A separate summary will also be presented by planned infusion number. A TEAE will be counted based on AE and infusion start dates. For example, if an AE starts after infusion #2 but before infusion #3, the AE will be counted under infusion #2.

If applicable, the incidence of anaphylactic reaction, defined as the broad algorithmic SMQ of “Anaphylactic reaction” given in [Appendix 13](#) will be summarized by treatment group.

In order to explore the temporal relationship of TEAEs that may be associated with the infusion, the incidence of all TEAEs occurring within 24 hours (1 day) of an infusion will be summarized by treatment group and presented in a listing. In addition, for this subset of TEAEs, the following will be summarized by treatment group for any infusion and at each infusion overall and by PT:

- the number and percent of subjects infused
- the number and percent subjects experiencing an event within 24 hours
- the number of the events
- descriptive statistics for the number of events per subject
- descriptive statistics for the duration (days) of the events

TEAEs will be counted as occurring within 24 hours (1 day) of an infusion if:

- the start date/time of the TEAE is not missing and the infusion start date/time \leq the start date/time of the TEAE \leq the infusion start date/time + 24 hours or
- the start time of the TEAE is missing and the TEAE start date = the infusion start date or the TEAE start date = the infusion start date + 1 day.

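### The anaphylactic reaction SMQ in SAP 9.2.1 has no time link to an infusion, so same-day heart-failure symptoms can be counted as anaphylaxis in either arm at any point in follow-up

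*SAP*

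**What the plan says.** Appendix 13 of the SAP sets the timing rule: "An Adverse Event or group of Adverse Events starting on the same day should be flagged as Anaphylactic Reaction per SMQ" if one of three conditions is met. These are "Any term from Group A"; "Any two terms, with one from Group B and one from Group C"; or "Any two terms, with one from Group D and one from either Group B or Group C". Nothing in the appendix refers to the date or time of an infusion.

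SAP 9.2.1, the section on infusion reactions, calls this rule: "If applicable, the incidence of anaphylactic reaction, defined as the broad algorithmic SMQ of" that name is summarized by treatment group. It adds no time condition. SAP 9.2 fixes the period: "All AE summaries will be restricted to TEAEs", which run from first dose to the last study visit or 30 days after the last dose, whichever is later.

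SAP 9.2.1 also defines an infusion window ("TEAEs will be counted as occurring within 24 hours (1 day) of an infusion if" the start falls within 24 hours of the infusion start or, when the event time is missing, on the infusion date or the next date). That window drives a separate summary of all TEAEs. The section does not apply it to the SMQ flag, and it names no listing of flagged subjects.

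**The concern.** Protocol 4.1 admits subjects with past or present signs and symptoms of heart failure. Breathlessness, swelling and low blood pressure can arise in such subjects without any drug reaction. Groups B, C and D contain Dyspnoea, Cough, Chest discomfort, Oedema, Swelling and Hypotension, and Group A contains Shock and Circulatory collapse. A same-day pair of such symptoms weeks after an infusion is tabulated as an anaphylactic reaction in the section on infusion reactions. The same holds months after the last dose, for a subject who stopped drug but kept attending visits.

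Few true events are to be expected. Protocol 1.3.2 reports infusion-related reactions with under 1% of infusions in the Phase 1/2 study, all Grade 1 or 2 and nonserious. With about 65 subjects per arm, a modest background could supply much of the count. A reader of the table could not tell how much of it is linked to an infusion.

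**Working it through.** The plan states no anaphylaxis rate or count, so there is no figure to reproduce. The check has three parts.

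**1. What the rule flags.** The Appendix 13 rule (A, or B with C, or D with B or C) was applied to example terms, using the lists as printed.

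| Terms starting on one day | Flagged? |
|---|---|
| Dyspnoea + Oedema | Yes (B + C) |
| Dyspnoea + Hypotension | Yes (D + B) |
| Cough + Hypotension | Yes (D + B) |
| Shock alone; Circulatory collapse alone | Yes (A) |
| Hypotension alone; Dyspnoea alone; Cardiac arrest alone | No |
| Cardiac failure; Cardiac failure + Hypotension | No |
| Dyspnoea + Oedema peripheral | No (Oedema peripheral not listed) |
| Orthostatic hypotension + Dyspnoea | No (Orthostatic hypotension not listed) |
| Pleural effusion + Dyspnoea; Cardiogenic shock | No |

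Decompensation is miscounted only when it is recorded as separate listed symptoms with one onset date, or as Shock or Circulatory collapse.

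**2. Share of follow-up inside the existing window.** Inputs: up to 12 infusions, one every 28 days (SAP 2.2.1); follow-up to 30 days after the last dose (SAP 9.2).

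- Infusion days: 1, 29, ..., 1 + 28 × 11 = 309. End of follow-up: 309 + 30 = Day 339.
- Calendar-date form (infusion date or next date): 12 × 2 = 24 days; 24/339 = 7.1%.
- Strict 24-hour form: 12/339 = 3.5%.

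If background flags are spread evenly, restriction removes about 93% of them (calendar-date form) to 96% (strict form).

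**3. Illustration of the dilution.** Inputs: 130 subjects at 1:1 (SAP 2.2.5), so 130/2 = 65 per arm. Assumed: background flag probability b = 5%, 10% or 20% per subject in each arm; true reactions t = 5% on NEOD001 and none on placebo, all inside the window; even timing of background flags.

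- Unrestricted: NEOD001 65 × [1 − (1 − b)(1 − t)]; placebo 65 × b.
- Restricted: the same with b replaced by b × 24/339.
- Example, b = 10%, unrestricted: 65 × [1 − 0.90 × 0.95] = 65 × 0.145 = 9.4 against 6.5. Restricted: b becomes 0.0071, giving 65 × 0.0567 = 3.7 against 0.5.
- True share among flagged NEOD001 subjects: t divided by the NEOD001 flag probability, e.g. 0.05/0.145 = 34%.

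| b | Unrestricted, NEOD001 v placebo | Difference | Ratio | True share | Restricted, NEOD001 v placebo | Difference | True share |
|---|---|---|---|---|---|---|---|
| 5% | 6.3 v 3.2 | 3.1 | 1.95 | 51% | 3.5 v 0.2 | 3.2 | 94% |
| 10% | 9.4 v 6.5 | 2.9 | 1.45 | 34% | 3.7 v 0.5 | 3.2 | 88% |
| 20% | 15.6 v 13.0 | 2.6 | 1.20 | 21% | 4.1 v 0.9 | 3.2 | 79% |

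Differences are 65 × t × (1 − b), with b restricted where applicable, computed before rounding. With b held at 10%, t = 3% gives 8.3 v 6.5 unrestricted and 2.4 v 0.5 restricted; t = 10% gives 12.3 v 6.5 and 6.9 v 0.5.

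The absolute excess stays near 3 subjects in every row of the table. What changes is the ratio and the meaning of the count.

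**The case against.** A reader might infer that heart-failure decompensation and hypotension in general are tabulated as anaphylaxis and that a real signal is buried. The documents do not support this.

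- Hypotension is a Group D term and never qualifies alone. Protocol 5.4.1 withholds drug for low blood pressure as a precaution and gives no frequency.
- Protocol 7.4.3 asks for serious events from disease progression to be reported by diagnosis, and neither of its examples (pleural effusion, acute heart failure) is in the printed lists. The common oedema event in the Phase 1/2 study was peripheral oedema, also not listed.
- Past heart-failure signs suffice for entry, and SAP 9.2 counts only events that newly appear, become more frequent or worsen, so stable baseline symptoms do not count.
- SAP 9.2.1 separately summarizes and lists infusion-associated TEAEs and all TEAEs within 24 hours of an infusion, by arm. A true reaction would appear in both if marked as infusion-associated and within the window.
- Randomization should balance the background, and SAP 9 plans no inferential safety comparison unless specified, so no planned test loses power.

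All of this stands, and it limits the point. It does not remove it. The reporting-by-diagnosis instruction concerns serious events, so nonserious worsening may still be entered as symptoms. Neither infusion-linked summary shows how many SMQ-flagged subjects fell inside the window; that would have to be rebuilt from listings.

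A further fair objection is that replacing the standard query by a windowed one would drop a Group A reaction starting after 24 hours from the table. That argues for showing both counts.

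**Conclusion.** The point holds as a limited specification gap in a descriptive safety table. Followed exactly, the plan counts certain same-day symptom pairs, and Shock or Circulatory collapse alone, as anaphylactic reactions whatever their distance from an infusion. This inflates the incidence in both arms and dilutes the relative contrast. It does not hide the absolute difference.

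The size cannot be fixed from the documents, which give no background flag rate; the 5% to 20% range and the true excess are assumptions. The 7.1% window share follows from the schedule for a subject who receives all 12 infusions. The 93% reduction also needs even timing. Adverse events are elicited at visits, and the Month 1 to 12 visits are normally infusion days, so clustering of recorded onsets on those days would leave more background inside the window and shrink the gain.

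**What to change.** In SAP 9.2.1 and Appendix 13, keep the unrestricted SMQ count. Beside it, by treatment group, add the number of SMQ-flagged subjects whose qualifying term or terms start within 24 hours of an infusion under the definition already in 9.2.1, including its rule for missing times. Add a listing of all flagged cases with the terms that triggered the flag and the time since last infusion.

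The cost is one sentence in the SAP, one table row and one listing. Later reactions stay in the unrestricted count, and no efficacy analysis is affected. The change should be made before unblinding.
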